8.4.3. Per-Protocol Cohort

The per-protocol cohort is a subset of the ITT subjects who receive a study stent(s) and no major protocol deviations (ICH E9 definitions).

8.5. *Analysis*

The following analyses are planned:

- Informal Interim Analysis (no hypothesis testing) once the first 50 subjects have reached 24 months post initial stent placement.
- Final Analysis after all subjects have reached 24 months post initial stent placement.

8.6. *Statistical Analysis*

All statistical analyses will be done using The SAS System software, version 8 or higher (Copyright © 2000 SAS Institute Inc., [name], USA. All rights reserved). Subject demographics, clinical history, risk factors, pre- and post-procedure characteristics and outcome variables will be summarized using descriptive statistics for continuous variables (mean, standard deviation, number of observations, minimum and maximum) and frequency statistics (percent of conformers, number of conformers, number of observations) for discrete variables.

8.6.1. Baseline Comparability

The baseline characteristics of subjects among centers and between treatments will be assessed using standard statistical tests. Any significant differences will be identified and investigated per SAP.

8.6.2. Post-Procedure Endpoints

Post-procedure information will be collected at regularly scheduled follow-up examinations as detailed in the clinical trial schedule and will be summarized using descriptive statistics for continuous variables and frequency statistics for discrete variables. Estimates of primary and secondary endpoints will be reported by treatment group, as well as differences between treatment groups and their 95% confidence intervals.

Impact of baseline variables on endpoints will be analyzed using logistic regression, ANOVA, stratified methods or Kaplan-Meier methods per section 8.6.1 and the SAP.

8.6.3. Pooling Across Institutions

The analyses will be presented using data pooled across institutions and poolability will be analyzed per the SAP.

9. Data Management

9.1. *Data Collection, Processing, and Review*

Subject data will be recorded in a limited access secure electronic data capture (EDC) system.

The clinical database will reside on a production server hosted by Medidata. All changes made to the clinical data will be captured in an electronic audit trail and available for review by Boston Scientific Corporation (BSC) or its representative. The associated RAVE software and database have been designed to meet regulatory compliance for deployment as part of a validated system compliant with laws and regulations applicable to the conduct of clinical studies pertaining to the use of electronic records and signatures. Database backups are performed regularly.

The Investigator provides his/her electronic signature on the appropriate electronic case report forms (eCRFs) in compliance with local regulations. A written signature on printouts of the eCRFs must also be provided if required by local regulation. Changes to data previously submitted to the sponsor require a new electronic signature by the Investigator acknowledging and approving the changes.

Visual and/or electronic data review will be performed to identify possible data discrepancies. Manual and/or automatic queries will be created in the EDC system and will be issued to the site for appropriate response. Site staff will be responsible for resolving all queries in the database.

9.2. *Data Retention*

The Investigator will maintain, at the investigative site, in original format all essential study documents and source documentation that support the data collected on the study subjects in compliance with ICH/GCP guidelines. Documents must be retained for at least 2 years after the last approval of a marketing application or until at least 2 years have elapsed since the formal discontinuation of the clinical investigation of the product. These documents will be retained for a longer period of time by agreement with BSC or in compliance with other local regulations. It is BSC's responsibility to inform the Investigator when these documents no longer need to be maintained. The Investigator will take measures to ensure that these essential documents are not accidentally damaged or destroyed. If for any reason the Investigator withdraws responsibility for maintaining these essential documents, custody must be transferred to an individual who will assume responsibility, and BSC must receive written notification of this custodial change.

10. Potential Risks and Benefits

10.1. *Anticipated Adverse Device Effects*

As per the commercial DFU included with the study devices, the potential complications associated with metal stent placement include, but are not limited to:

- Pain
- Bleeding
- Fever
- Nausea
- Vomiting
- Infection
- Inflammation
- Stent occlusion
- Tumor overgrowth around ends of stent
- Tumor ingrowth through the stent
- Mucosal hyperplasia
- Cholangitis
- Cholecystitis*
- Pancreatitis
- Ulceration of duodenum or bile duct
- Perforation of duodenum or bile duct
- Stent migration
- Death (other than that due to normal disease progression)
- Stent misplacement
- Perforation of the gallbladder due to the stent covering the cystic duct*
- Stent Fracture
- Hepatic abscess

*Note: In a small clinical trial of this device, two out of four (50%) subjects who had a stent placed across the cystic duct developed cholecystitis. One of these subjects suffered a perforated gallbladder due to the stent covering the cystic duct, requiring a drain to be placed.

As per the commercial DFU included with the study devices, potential complications associated with stent removal include, but are not limited to:

- Pain
- Bleeding
- Fever
- Nausea
- Vomiting
- Infection
- Inflammation
- Recurrent obstructive jaundice
- Mucosal hyperplasia
- Cholangitis
- Cholecystitis
- Pancreatitis
- Ulceration of duodenum or bile duct
- Perforation of duodenum or bile duct

- Death (other than that due to normal disease progression)
- Impaction to the common bile duct wall

The following specific definitions will be used:

- Pancreatitis: Abdominal pain and a serum concentration of pancreatic enzymes (amylase or lipase) three or more times the upper limit of normal, that required more than one night of hospitalization
- Cholecystitis: No suggestive clinical or radiographic signs of cholecystitis before the procedure and if emergency cholecystectomy is subsequently required
- Perforation: Retroperitoneal or bowel-wall perforation documented by any radiographic technique or direct visual evidence
- Stent Occlusion: Recurring obstructive jaundice with necessary stent replacement
- Hepatic Abscess: Intra-hepatic fluid collection with positive cultures identified when possible by ultrasonography or computed tomography, associated with persistent fever and elevations of white blood cells
- Cholangitis: Elevation in temperature more than 38°C, thought to have a biliary cause, without concomitant evidence of acute cholecystitis, requiring intervention
- Bleeding: Bleeding requiring endoscopic hemostatic intervention and/or transfusion

10.2. Risk Minimization Actions

Additional risks may exist. Risks can be minimized through compliance with this protocol, performing procedures in the appropriate hospital environment, adherence to subject selection criteria, close monitoring of the subject's physiologic status during research procedures and/or follow-ups and by promptly supplying BSC with all pertinent information required by this protocol.

10.3. Anticipated Benefits

Subjects may not receive any benefit from participating in this study. However, medical science and future subjects may benefit from this study.

10.4. Risk to Benefit Rationale

Based on prior BSC clinical studies and collected reports in literature to-date, the risk-to-benefit ratio is within reason for foreseeable risks. However, literature reports do not always capture all side effects. Observation and follow-up of subjects is required as outlined in the protocol.

11. Safety Reporting

11.1. Definitions and Classification

Adverse event definitions are provided in Table 11.1-1.

Table 11.1-1: Adverse Event Definitions

Term	Definition
------	------------

Table 11.1-1: Adverse Event Definitions

Term	Definition
Adverse Event (AE) Ref: ISO 14155-2011	Any untoward medical occurrence, unintended disease or injury, or untoward clinical signs (including abnormal lab findings) in subjects, users or other persons, whether or not related to the investigational medical device. This includes events related to: 
 • The investigational medical device or comparator • The procedures involved (study-required) For users/other persons, this definition is restricted to events related to the investigational device
Adverse Device Effect (ADE) Ref: ISO 14155-2011	Adverse event related to the use of an investigational medical device: 
 • This includes adverse events resulting from insufficient or inadequate instructions for the use, deployment, implantation, installation or operation, or any malfunction of the investigational medical device. • This includes any event resulting from use error or from intentional misuse of the investigational medical device.
Serious Adverse Event (SAE) Ref: ISO 14155-2011	An adverse event that: 
 • Led to death • Led to a serious deterioration in the health of the subject that either resulted in: 
 ○ a life-threatening illness or injury, or ○ a permanent impairment of a body structure or a body function, or ○ in-patient hospitalization or prolonged hospitalization (of an existing hospitalization), or ○ medical or surgical intervention to prevent life-threatening illness or injury or permanent impairment to a body structure or a body function • Led to fetal distress, fetal death, or a congenital abnormality or birth defect. 
Note: Planned hospitalization for a pre-existing condition, or a procedure required by the protocol, without serious deterioration in health, is not considered a serious adverse event.
 
Note: For SAE reporting requirements see the information below for SADE.

Serious Adverse Device Effect (SADE) Ref: ISO 14155-2011	An adverse device effect that has resulted in any of the consequences characteristic of a serious adverse event. 
Note: All SAEs that could have led to a SADE if suitable action had not been taken or if circumstances had been less fortunate shall be reported as required by the local IRB/EC, national regulations, or the protocol. If applicable, see MEDDEV 2.7/3 12/2010 for reporting timeline requirements.

Device Deficiency Ref: ISO 14155-2011 Ref: MEDDEV 2.7/3 12/2010	A device deficiency is any inadequacy of a medical device with respect to its identity, quality, durability, reliability, safety or performance. 
Note: Device deficiencies include malfunctions, use errors, and inadequate labeling.
 
Note: All device deficiencies that could have led to a SADE if suitable action had not been taken or if circumstances had been less fortunate shall be reported as required by the local IRB/EC, national regulations, or the

Table 11.1-1: Adverse Event Definitions

Term	Definition
	protocol. If applicable, see MEDDEV 2.7/3 12/2010 for reporting timeline requirements.

Abbreviations: EC=Ethics Committee; IRB=Institutional Review Board

Underlying diseases are not reported as AEs unless there is an increase in severity or frequency during the course of the investigation. Death should not be recorded as an AE, but should only be reflected as an outcome of a specific SAE (see Table 11.1-1 for AE definitions).

Any AE experienced by the study subject after informed consent, whether during or subsequent to the procedure, must be recorded in the eCRF.

Refer to Section 10.1 for the known risks associated with the study device(s).

11.2. Relationship to Study Device(s)

The Investigator must assess the relationship of the AE to the study device as related or unrelated. See criteria in Table 11.2-1.

Table 11.2-1: Criteria for Assessing Relationship of Study Device to Adverse Event

Classification	Description
Unrelated	The adverse event is determined to be due to a concurrent illness or effect of another device/drug and is not related to the investigational product.
Related	
 • The adverse event is determined to be potentially related to the investigational product, and an alternative etiology is equally or less likely compared to the potential relationship to investigational product. • There is a strong relationship to investigational product, or recurs on re-challenge, and another etiology is unlikely. • There is no other reasonable medical explanation for the event.

11.3. Investigator Reporting Requirements

11.3.1. Serious Adverse Events

These events should be reported to the Global Safety Office and/or Project Manager **within 2 business days** of first becoming aware of the event. Events should be documented in the eCRF and all relevant source documentation for the event should be provided to the Global Safety Office, as applicable.

11.3.2. Adverse Events

Device and procedure-related events should be reported to the Global Safety Office and/or Project Manager **within 10 business days** of first becoming aware of the event. Unrelated AEs will not be collected.

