4.2. Secondary Endpoints

1. Occurrence of adverse events related to the stent and/or the stent placement or removal procedures
2. Number of ERCP procedures through 24 months after initial stent placement
3. Ability to deploy the stent(s) in satisfactory position
4. Stent Removal:
 - Ability to remove the stent(s) without serious stent removal related adverse events at each procedure involving removal of stent(s) (technical success at removal) or
 - Complete distal migration without serious stent removal related adverse events
5. Liver Function Tests (LFT's)
 - Baseline LFTs compared to LFTs taken at time of original plastic stent placement for any subject with a prior plastic stent
 - LFT improvement at 1 month post-study treatment compared to baseline LFTs (and/or compared to LFTs taken at time of original plastic stent placement for any subject with a prior plastic stent)
 - LFTs at month 24 compared to LFTs at removal of last stent (applicable for subjects who had not been re-stented at time of month 24 visit)
6. Health Economic Endpoints:
 - Number of outpatient procedures
 - Number of hospitalizations
 - Duration of hospitalizations

- Length of procedures
- Number of devices

5. Design

The study is designed as a post-market, multi-center, prospective, non-blinded, randomized study. At least 164 subjects (82 per arm) will be treated with 1:1 randomization between Group A and Group B and will be followed through 24 months post-initial stent(s) placement:

- Subjects in the MS arm will be treated with a single metal stent, which will be removed 12 months post-placement.
- Subjects in the PS arm will receive 2 plastic stents when possible. Subjects in this arm will undergo plastic stents exchange/bile duct calibration at 4 and 8 month post-initial stent placement. At each stent exchange, the goal should be to provide progressive stent therapy by increasing the number of plastic stents at 4 months and again at 8 months. Final plastic stent removal will occur 12 months post-initial stent placement.

5.1. Inclusion Criteria:

- Age 18 or older
- Willing and able to comply with the study procedures and provide written informed consent to participate in the study
- Chronic pancreatitis

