- Record, report and assess (seriousness and relationship to the device/procedure) every adverse event and observed device deficiency.
- Report to BSC, per the protocol requirements, all SAEs and device deficiencies that could have led to a SADE.
- Report to the IRB/EC and regulatory authorities any SAEs and device deficiencies that could have led to a SADE, if required by the national regulations or this protocol or by the IRB/EC, and supply BSC with any additional requested information related to the safety reporting of a particular event.
- Maintain the device accountability records and control of the device, per local requirements, ensuring that the investigational device is used only by authorized/designated users and in accordance with this protocol and instructions/directions for use.
- Allow the sponsor to perform monitoring and auditing activities and be accessible to the monitor and respond to questions during monitoring visits.
- Allow and support regulatory authorities and the IRB/EC when performing auditing activities.
- Ensure that informed consent is obtained in accordance with this protocol and local IRB/EC requirements.

- Provide adequate medical care to a subject during and after a subject's participation in a clinical study in the case of adverse events, as described in the Informed Consent Form (ICF).
- Inform the subject of the nature and possible cause of any adverse events experienced.
- As applicable, provide the subject with necessary instructions on proper use, handling, storage, and return of the investigational device when it is used/operated by the subject.
- Inform the subject of any new significant findings occurring during the clinical investigation, including the need for additional medical care that may be required.
- Provide the subject with well-defined procedures for possible emergency situations related to the clinical study and make the necessary arrangements for emergency treatment, including decoding procedures for blinded/masked clinical investigations, as needed.
- Ensure that clinical medical records are clearly marked to indicate that the subject is enrolled in this clinical study.
- Ensure that, if appropriate, subjects enrolled in the clinical investigation are provided with some means of showing their participation in the clinical investigation, together with identification and compliance information for concomitant treatment measures (contact address and telephone numbers shall be provided).

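### The protocol both requires every adverse event to be recorded and says unrelated ones are not collected, and its relatedness criteria do not match the safety endpoint

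*Protocol*

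**What the plan says.** On recording, Protocol 11.1 is unconditional: "Any AE experienced by the study subject after informed consent, whether during or subsequent to the procedure, must be recorded in the eCRF". Protocol 15.2 repeats the duty for investigators: "Record, report and assess (seriousness and relationship to the device/procedure) every adverse event and observed device deficiency". Protocol 11.3.2 first sets a 10-business-day reporting time for one class of event ("Device and procedure-related events should be reported to the Global Safety Office and/or Project Manager") and then ends: "Unrelated AEs will not be collected". Protocol 11.3.1 handles serious adverse events separately. They are reported within 2 business days and documented in the eCRF, with no condition on relatedness.

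On relatedness, Protocol 11.2 makes a two-way judgement against the device: the investigator "must assess the relationship of the AE to the study device as related or unrelated". Table 11.2-1 defines the unrelated class as: "The adverse event is determined to be due to a concurrent illness or effect of another device/drug and is not related to the investigational product".

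On use, secondary endpoint 1 (Protocol 4.2, SAP 5.1) is: "Occurrence of adverse events related to the stent and/or the stent placement or removal procedures". Complication rates are also named in the primary objective (Protocol 3). SAP 7.3 compares adverse events between arms with two-sided exact tests. Protocol 5 describes the study as non-blinded.

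**The concern.** There are two separate problems. First, the collection rules conflict, so the content of the adverse-event database depends on which section a site follows. Secondly, the criteria that would decide whether an event counts as related do not fit the endpoint they feed. They cover neither the placement, exchange and removal procedures nor, clearly, the plastic stent.

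At stake is the credibility of the complication comparison. An investigator who knows the arm makes the attribution, and the documents describe no independent adjudication. The usual safeguard is to compare all events regardless of attribution and see whether the picture changes. If unrelated non-serious events are never entered, that safeguard is lost for them. The gap cannot be closed from the study database at the analysis stage.

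**Working it through.** The documents state no adverse-event rate or power, so there is no figure to reproduce. The main check sets the sections side by side.

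**Step 1: what happens to each kind of event.**

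| Event | 11.1 and 15.2 | 11.3.1 | 11.3.2 |
|---|---|---|---|
| Serious, related or not | record | report, document in eCRF | – |
| Non-serious, device- or procedure-related | record | – | report |
| Non-serious, unrelated | record | – | do not collect |

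Only the last row conflicts. The final sentence of 11.3.2 cannot be read as a mere reporting deadline, because the deadline is in the sentence before it and the final one is about collection.

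**Step 2: do the criteria match the endpoint?**

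- Endpoint 1 needs relation to the stent, to placement and to removal, in both arms.
- Protocol 11.3.2 and 15.2 name procedure-related events, so the category exists, but no criteria for it are given.
- Table 11.2-1 is worded for an investigational product and puts the effect of another device in the unrelated class. Protocol 14 says no investigational devices are used, while the adverse-event definition in Table 11.1-1 includes the comparator. The classification of a plastic-stent event is therefore left to interpretation.
- The plastic-stent arm has scheduled exchanges at Months 4 and 8 that the metal-stent arm does not have (Protocol 5, Table 1). By design it has more of the procedures that lack criteria.

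**Step 3: how much could unequal attribution matter?** This is an illustration only. Let p be the true event risk, equal in both arms, and r1 and r2 the share of events called related in each arm. The observed risks are p × r1 and p × r2. The rejection probability is the sum, over all pairs (x, y) with two-sided Fisher p ≤ 0.05, of Bin(x; 82, p × r1) × Bin(y; 82, p × r2). The 82 per arm comes from Protocol 5. The values of p, r1, r2 and the 0.05 level are assumptions; the SAP states no level for this test.

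| p | r1 v r2 | Observed risks | Rejection |
|---|---|---|---|
| 30% | 100% v 100% | 30% v 30% | 3.4% |
| 30% | 80% v 80% | 24% v 24% | 3.2% |
| 30% | 90% v 80% | 27% v 24% | 5.0% |
| 30% | 80% v 70% | 24% v 21% | 5.0% |
| 30% | 100% v 80% | 30% v 24% | 10.4% |
| 30% | 100% v 70% | 30% v 21% | 20.8% |
| 30% | 100% v 60% | 30% v 18% | 36.9% |
| 50% | 90% v 80% | 45% v 40% | 7.2% |
| 50% | 80% v 60% | 40% v 30% | 21.8% |

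Equal attribution leaves the test below its level. A 10-point gap takes it to about 5% to 7%. Large gaps take it well above.

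**Step 4: what the table does and does not measure.** Endpoint 1 counts related events by definition. An event judged unrelated is left out of it whether or not it was stored. The rejection rates in Step 3 are therefore the effect of unequal attribution and would be the same under full collection. Non-collection adds something different: it removes the data against which attribution could be checked.

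**The case against.** The strongest reply is that collecting all serious events plus related non-serious ones is a coherent choice for a post-market study. On that view the conflict is a drafting slip, which could equally be removed by narrowing 11.1 and 15.2. That is fair as to the choice of rule. It does not excuse leaving two incompatible rules in force.

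A reader might infer that the bias in the complication comparison is beyond recovery. The documents do not support that. Serious events enter the eCRF regardless of cause (Protocol 11.3.1). Several of the complications defined in Protocol 10.1 would often be serious: pancreatitis requires more than one night in hospital, and cholecystitis requires emergency cholecystectomy. Additional ERCPs, hospitalizations and scheduled symptom assessments also leave traces independent of attribution. The loss concerns non-serious events only, and only at sites that follow 11.3.2.

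A reader might also infer that procedure complications not blamed on the device would drop out. The opening sentence of 11.3.2 names procedure-related events as reportable, and 15.2 asks for relation to device or procedure. Read in context, unrelated most naturally means related to neither. What remains is that no criteria guide the procedure judgement.

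Finally, a reader might take the 10% to 37% rejection rates as the price of not collecting unrelated events. They are not, as Step 4 shows. They also assume complete capture in one arm and a 20% to 40% loss in the other, a pattern for which the documents give no basis.

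**Conclusion.** The point holds in limited form. The conflict between 11.1 and 15.2 on one side and 11.3.2 on the other is literal and affects non-serious unrelated events. The relatedness criteria do not cover the procedures in endpoint 1 and leave the plastic stent's status unclear. Together with unblinded assessment by the investigator, this removes the all-cause check on attribution for non-serious events. The all-cause check for serious events survives, although the SAP does not plan it. If every site followed 11.1 and 15.2, nothing would be lost, but the protocol does not secure that.

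The textual findings need no assumption. The size of any bias cannot be fixed from the documents. At an assumed 30% risk and 0.05 level, false-positive rates run from about 3% with equal attribution, through 5% with a 10-point gap, to 37% at the one-sided extreme. These figures describe attribution, not collection. The primary endpoint, stricture resolution, is not affected.

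**What to change.** 1. State one collection rule in identical words in Protocol 11.1, 11.3.2 and 15.2. Deleting the last sentence of 11.3.2 is the simplest way. If full collection is judged too burdensome, at least collect all biliary and ERCP-type events regardless of attribution, and narrow 11.1 and 15.2 to match.
2. Reword Protocol 11.2 and Table 11.2-1 to cover the metal and the plastic stents by name, and to code relation separately to the stent, to the placement or exchange procedure and to the removal procedure, with criteria for each.
3. Keep related events as secondary endpoint 1. Add to the SAP a by-arm comparison of all-cause serious events, and of all collected adverse events, as a sensitivity analysis on attribution.

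This does not remove attribution bias from the endpoint; it makes the bias visible. The cost is a protocol and eCRF amendment, a few SAP tables and some extra non-serious entries at sites. It is worth doing before or during data collection, because events not entered cannot be analysed later.
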